1.9.4 Benefit/Risk Ratio

The anticipated risks, based on the non-clinical experience with the CyPep-1 injectable solution and the clinical experience with the standard of care anti-PD-1 antibody pembrolizumab, are expected to be manageable. The importance of the objective of this trial is considered to outweigh the risks and burdens to the subjects. Measures are implemented to minimize burdens and risks for subjects. Subjects will be monitored closely for the occurrence of any significant clinical events and treatment will only continue if it is considered safe and appropriate to do so. The benefit/ risk assessment is favorable and justifies the planned trial in subjects with solid tumors at a situation with no therapeutic options available.

2. TRIAL OBJECTIVES AND ENDPOINTS

2.1 Objectives

2.1.1 Primary Objectives

The primary objectives are:

- To evaluate the safety and tolerability of intratumoral administration of CyPep-1, as monotherapy and in combination with pembrolizumab.
- To identify the recommended phase II dose (RP2D) of CyPep-1, as monotherapy and in combination with pembrolizumab.

2.1.2 Secondary Objectives

The secondary objectives are:

- To assess the preliminary anti-tumor efficacy of CyPep-1, as monotherapy and in combination with pembrolizumab.
- To characterize the pharmacokinetics (PK) of CyPep-1.

2.1.3 Exploratory Objectives

The exploratory objectives are:

- To assess the preliminary anti-tumor efficacy of CyPep-1, as monotherapy and in combination with pembrolizumab, in injected lesions and non-injected lesions, separately.
- To assess survival after treatment with CyPep-1, as monotherapy and in combination with pembrolizumab.
- To assess the immune modulating properties of treatment with CyPep-1, as monotherapy and in combination with pembrolizumab.

2.2 Endpoints

2.2.1 Primary Endpoints

The primary endpoints are:

- Type and number of AEs according to National Cancer Institute (NCI) – Common Terminology Criteria for Adverse Events (CTCAE) criteria v5.0, and additional safety parameters of CyPep-1 as monotherapy and in combination with pembrolizumab.
- Dose limiting toxicities (DLTs) and the maximum tolerated dose (MTD) for determination of RP2D of CyPep-1 as monotherapy and treatment-limiting toxicities (TLTs) of CyPep-1 in combination with pembrolizumab.

2.2.2 Secondary Endpoints

The secondary endpoints are:

- Objective response rate (ORR), defined by complete and partial responses, according to immune Response Evaluation Criteria in Solid Tumors (iRECIST) based on the investigator's assessment.
- Time to and duration of response and duration of stable disease.
- The plasma concentration time profile of CyPep-1 and, if detectable, the derived PK parameters (i.e., area under the curve [AUC], peak plasma concentration [C_{max}], time to reach C_{max} [t_{max}], systemic clearance [CL], elimination half-life [$t_{1/2}$] and volume of distribution [VD]).

2.2.3 Exploratory Endpoints

The exploratory endpoints are:

- For all Phase IIa arms: ORR in injected lesions and non-injected lesions, separately, per itRECIST* [[Goldmacher 2020](#)]).
- Progression-free survival (PFS) per iRECIST based on the investigator's assessment.
- Overall survival (OS).
- The relative change in number of tumor infiltrating CD8+ T-cells in the injected and, whenever available, non-injected tumor biopsies.
- The association between the relative change in tumor infiltrating CD8+ T-cells and response rate in the injected lesions (per itRECIST) and all lesions (per iRECIST). The change in T-cell receptor (TCR) clonality levels in peripheral blood and (when available) biopsied lesions.
- Changes in the tumor microenvironment (injected and, whenever available, non-injected tumor biopsies) via expression of selected candidate immune markers:
[REDACTED]
[REDACTED]
[REDACTED]
- For Arms A, B, and C: [REDACTED]
[REDACTED]
- Peripheral blood phenotyping of selected immune cell markers.

[figure not shown]
*itRECIST will be programatically calculated using data obtained from iRECIST assessments following the itRECIST principle summarized in [Appendix F Figure 1](#).

3. TRIAL DESIGN

3.1 Overall Trial Design

This is a combined Phase I/Illa, open-label, dose escalation followed by dose expansion trial in subjects with advanced solid cancers. The trial consists of two phases and multiple arms, as shown in the diagram below ([Figure 2](#)).

Figure 2. Schematic trial design

Phase I (dose escalation, N=12) and Phase IIa (dose expansion Arm A N=9*; combination Arm B N=15 and dose expansion liver metastases Arm C, N=9; dose expansion melanoma Arm D, N= 30).

Abbreviations: RP2D: recommended phase 2 dose.

*In case in the first 12 subjects at RP2D, a responder per iRECIST (ORR based on best response or 2 subjects with stable disease per iRECIST are observed (SD based on duration >16 weeks from onset of SD), the number of subjects will be expanded to a total of 24 (CyPep-1 monotherapy; cohort 3 of Phase I and in Phase IIa Arm A).

Phase I—dose escalation:

In this phase of the trial, safety and tolerability will be documented and the MTD/RP2D will be determined. Cohorts of 3 subjects will receive intratumoral injections with CyPep-1. The DLT observation period for each dose level will be 6 weeks (5 weeks of trial treatment and 1 week of safety follow-up). The following CyPep-1 administrations are planned as continuous Q2W administrations.

Screening will occur during the 4 weeks prior to start of CyPep-1 treatment.

In three dose cohorts of 3 subjects each, subjects will receive CyPep-1 intratumorally at different concentrations (dose escalation) and volumes (depending on tumor size), i.e.,

0.5 mg/mL, 2 mg/mL, or 5 mg/mL, respectively. These dose concentrations have been selected based on previous preclinical experience with CyPep-1.

Dose escalation (Phase I of the trial) will be conducted to determine the MTD or RP2D using a standard “3+3” design, with at least three subjects treated at each dose-level. Arm C (from Phase IIa) will follow a similar dose escalation of two dose levels (RP2D and the dose immediately below). Dose escalation will proceed according to the following rules:

Number of subjects with DLT*	Escalation decision rule
0 out of 3 subjects	Enter 3 subjects at the next planned dose level.
1 out of 3 subjects	Enter 3 additional subjects at this dose level: 
• If 0 of these additional subjects experience a DLT, proceed to the next dose level.• If 1 or more of the additional 3 subjects experience a DLT, then dose escalation to higher dose levels is stopped. Three additional subjects may be entered at the second highest dose if only 3 subjects have been treated at that dose level. Alternatively, a new dose level may be introduced between the second highest dose and the MTD (3 additional subjects).
≤ 1 out of 6 subjects at the highest dose level below the MTD	This dose level is declared the MTD or RP2D.

*Assessed as related to the trial drug (CyPep-1) at any given dose level.

Each subject will receive IT injection(s) with CyPep-1 in Week 1, 3, and 5, respectively. After each CyPep-1 administration, subjects will be required to stay at the clinic for at least 4 hours for safety and, for those in which PK will be assessed, also for PK monitoring. The data from the additional three subjects in cohort 3 will be used for further confirmation of RP2D.

For each dose cohort, at least 24 hours must elapse between each subject to start treatment with CyPep-1. No intra-subject dose escalation is allowed.

In Phase I, subject replacement for subjects that drop out for any reason, except DLTs, will only occur before the DLT observation period is completed and is allowed if a subject does not receive all three CyPep-1 administrations, unless due to CyPep-1-related toxicity. No subject replacement will occur for subjects who withdraw later.

After completion of Phase I, all results will be evaluated by the DEC. This will include safety data and if available, other supportive clinical data (i.e. efficacy, pharmacokinetics, tumor biopsy analyses) from all subjects included in Phase I of the trial. The DEC will confirm the MTD or RP2D (in case the MTD is not reached).

All additional arms of the CICILIA trial can start once Phase I data has been evaluated by the DEC and an MTD or RP2D is confirmed for CyPep-1.

Phase IIa – dose expansion (Arm A):

In this phase, safety and tolerability will be further evaluated in an expanded cohort of 9 subjects at the RP2D of CyPep-1, determined in Phase I. Screening and CyPep-1

administration will be according to the schedule described for Phase I, except for the 24-h observation period before start of treatment of the next subject, which is not applicable.

In case in the first 12 subjects at RP2D, a responder per iRECIST (ORR as CR/PR as best response) or 2 subjects with stable disease (SD with duration >16 weeks from onset) per iRECIST are observed, the number of subjects will be expanded to a total of 24 (CyPep-1 monotherapy; subjects cohort 3 of Phase I and in Phase IIa Arm A).

Phase IIa – combination arm (Arm B):

The safety and tolerability of CyPep-1 in combination with pembrolizumab will be evaluated in a cohort of 15 subjects in total, using a staggered approach. Initially, 3 subjects will receive CyPep-1 at RP2D in combination with pembrolizumab and each subject will be observed for 24 h before the next subject can be administered with CyPep-1. After the first 3 subjects completed the TLT observation period of 6 weeks with no TLTs observed and after reviewing the safety data (including TLTs) by the DEC, the inclusion of all remaining subjects at RP2D of CyPep-1 in combination with pembrolizumab can be initiated. In the absence of any TLTs, the 24-h observation period before start treatment of the next subject is no longer applicable. Should any TLTs be observed in the first 3 subjects at the RP2D of CyPep-1 in combination with pembrolizumab, an additional 3 subjects will be included in this dose group. If ≤1 out of 6 subjects have a TLT, the remainder of the 15 subjects will be treated at the RP2D. In the unlikely case that 2 or more of the 6 subjects experience any TLTs at RP2D of CyPep-1, a recommendation to dose de-escalate and to what dose or to continue the combination part of the trial will be made by the DEC. The same screening is planned, and CyPep-1 will be administered according to the same schedule as in Phase I.

Scheduling of treatment of CyPep-1 and pembrolizumab (Arm B) will be as follows: CyPep-1 will be administered every 2 weeks (Q2W) and pembrolizumab will be administered following a Q6W schedule starting on Day 1, as per standard of care. Radiological assessment to determine occurrence of (un)confirmed PD will be performed Q8W from the start of treatment. Treatment will continue until confirmed PD, unacceptable toxicity or consent withdrawal, loss to follow up, or trial end, whichever occurs first.

Phase IIa – dose expansion liver metastases (Arm C):

The safety and tolerability of at least two dose levels of CyPep-1, namely the RP2D and the dose immediately below that, are planned to be evaluated when CyPep-1 is administered intratumorally using ultrasound guidance to one metastatic lesion in the liver. The two dose levels are planned to be investigated adhering to the 3+3 design and will follow the procedures as described for the dose escalation (Phase I) (Section 3.1). The first three subjects will receive CyPep-1 at the lower dose level and each subject will be observed for 24 h before CyPep-1 administration to a next subject (cohort 4). After the third subject at that dose finished the DLT observation period of 6 weeks (5 weeks CyPep-1 treatment plus 1 week safety follow-up), the DEC will decide on the start of the cohort to be administered at RP2D based on the review of the safety data (cohort 5). In the absence of any DLTs in the first 3 subjects, the 24-h observation period before start treatment of the next subject is not applicable. After the DLT observation period for the first three subjects at RP2D for CyPep-1 and the review of all safety data, the DEC will recommend on the inclusion of all remaining subjects. Should a DLT be observed in the first three subjects at the RP2D of CyPep-1, an additional three subjects in this dose group will be included. In case that two or more subjects experience DLTs at RP2D of CyPep-1, a recommendation to dose de-escalate and to what dose and how to continue Arm C will be made by the DEC.

Phase IIa – dose expansion melanoma subjects (Arm D):

The safety and tolerability of CyPep-1 at RP2D will be further evaluated with focus on assessing efficacy signals of CyPep-1 monotherapy in up to 30 subjects with melanoma. Although safety information will be collected, there will not be a formal DLT observation period. The dosing scheme starts with a once weekly (QW) CyPep-1 administration until the second iRECIST/itRECIST assessment at week 16, followed by a Q2W dosing scheme.

As part of the continuous safety monitoring of the trial, reports with cumulative safety data of Arm D subjects will be shared with all investigators, competent authorities, and ethical committees of countries where the trial is conducted at the following time points:

- After the first three subjects completed three weeks of treatment with CyPep-1.
- After the first three, six, and 12 subjects completed six weeks of treatment with CyPep-1.

In the occurrence of AEs fulfilling DLT criteria or other safety alters, the DEC will convene to review the safety data and provide recommendations on the continuation of dosing.

For both phases and all trial arms, subjects will stay in the trial until end of trial or until confirmed disease progression, unacceptable toxicity, death or discontinuation for any other reason. Information regarding subject replacement for each arm is detailed in [Section 4.3.2](#).

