3.1.1 Dose Escalation Committee

The decisions on dose escalation and CyPep-1 MTD/RP2D will be taken by the Dose Escalation Committee (DEC) after reviewing safety data (including DLTs) from all subjects who have entered Phase I of the trial and have completed the DLT observation period.

The DEC will review all data after all subjects in the highest dose cohort completed DLT observation period and before enrolment of subjects in the expansion cohort at RP2D in monotherapy and combination with pembrolizumab cohort can be initiated.

For Phase IIa of the trial, the decision to de-escalate the dose of CyPep-1 based on observed the severity and relatedness of safety events (DLT/TLT criteria for CyPep-1) and to what dose (either dose level of the next lowest dose level from Phase I or 50-70% of current dose level), will also be made by the DEC after reviewing available safety data (including TLTs). Dose modifications for pembrolizumab in the combination arm will also be taken into consideration (refer to [Section 5.3.6](#)).

Based on the review of this data, recommendations will be made regarding the further conduct and the scientific and ethical integrity of the trial.

The DEC is comprised of all the investigators or designees, as well as the medical monitor and representatives of the sponsor. The DEC, chaired by the medical monitor, will strive for a consensus opinion regarding the data reviewed. If DEC consensus is not possible, the DEC chair will assemble and present majority and dissembling opinions for all recommendations considered. If any of the DEC members cannot be present during the meeting due to the short notice, the DEC will be held (not postponed) provided that a minimum of 2 members are present. The DEC members may be allowed to provide their recommendations electronically to the DEC chair, prior to the meeting.

At the end of the DEC teleconference, the DEC will provide one of the following recommendations to the sponsor:

1. The trial is proceeding in line with the trial protocol.
2. The trial is not proceeding in line with the trial protocol and/or there is a possible change in the benefit/risk ratio.

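### Arm B doses three more subjects at the same level even after 2 or 3 of the first 3 have a TLT, when referral to the DEC is already certain

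*Protocol*

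**What the plan says.** Protocol Section 3.1 (Phase IIa, Arm B) starts three subjects on CyPep-1 at the RP2D with pembrolizumab. Once they have "completed the TLT observation period of 6 weeks with no TLTs observed and after reviewing the safety data (including TLTs) by the DEC", the remaining subjects may enter.

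If there are TLTs, the rule is: "Should any TLTs be observed in the first 3 subjects at the RP2D of CyPep-1 in combination with pembrolizumab, an additional 3 subjects" join the same dose group. Two outcomes follow. With at most 1 TLT in 6, the rest of the 15 are treated at the RP2D. The other outcome begins "In the unlikely case that 2 or more of the 6 subjects experience any TLTs at RP2D of CyPep-1"; the DEC then recommends either de-escalating, and to what dose, or continuing.

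The same rule appears in the protocol synopsis and in SAP Section 6.1. None of the three places has a separate branch for 2 or 3 TLTs among the first 3 subjects.

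**The concern.** The expansion step of a 3+3 rule exists to resolve one toxicity in three, which is ambiguous. With two or three in three there is nothing left for it to resolve: the threshold for continuing has already been exceeded. The Arm B text still sends the next three subjects to the same dose, and ties the DEC recommendation to a count out of six.

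Referral to the DEC is not a stop. The committee may recommend continuing, and three more subjects could inform that choice. The problem is the order, because dosing is written to come before the review.

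TLTs are serious events. Section 3.1.2 includes Grade 4 non-hematologic toxicity and Grade 5 toxicity. Section 7.1.3.1 also names the staggered start of this arm as a measure against tumor lysis syndrome, so the run-in rule has a safety function.

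**Working it through.** **Inputs.** From Section 3.1: a first group of 3, an added group of 3, continuation at ≤1 of 6, referral at ≥2 of 6. The documents give no operating characteristics for this rule and no TLT rate for the combination, so there is no plan figure to reproduce. The true rate *p* is an assumption, shown from 10% to 50%.

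**Step 1: can the added three change the branch?** Let X be the number of TLTs in the first 3 and Y the number in the next 3, each binomial(3, *p*) and independent.

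- X = 1: P(X+Y ≤ 1) = P(Y = 0) = (1−*p*)³, for example 0.8³ = 51.2% at *p* = 20%. The added three decide the branch.
- X = 2 or 3: X+Y ≥ 2 whatever Y is, so P(X+Y ≤ 1) = 0 at every *p*. They cannot change the branch.

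**Step 2: how often, and at what cost?**

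- P(X ≥ 2) = 3*p*²(1−*p*) + *p*³
- Expected TLTs in three more subjects = 3*p*
- P(clear RP2D) = P(X=0) + P(X=1)·P(Y=0)
- P(referral) = 1 − P(clear)
- Share of referrals already certain after subject 3 = P(X ≥ 2) / P(referral)

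Worked at *p* = 20%: P(X ≥ 2) = 3(0.04)(0.8) + 0.008 = 0.104. P(clear) = 0.512 + 0.384 × 0.512 = 0.709. P(referral) = 0.291. Share = 0.104 / 0.291 = 36%.

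| Assumed TLT rate | P(2–3 TLTs in first 3) | Expected TLTs in the added 3 | P(clear RP2D) | P(referral) | Share certain after subject 3 |
|---|---|---|---|---|---|
| 10% | 2.8% | 0.3 | 90.6% | 9.4% | 30% |
| 20% | 10.4% | 0.6 | 70.9% | 29.1% | 36% |
| 33.3% | 25.9% | 1.0 | 42.8% | 57.2% | 45% |
| 50% | 50.0% | 1.5 | 17.2% | 82.8% | 60% |

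**Step 3: effect of restricting expansion to X = 1.** P(clear) and P(referral) are identical under both rules, because X ≥ 2 never clears. Expected subjects treated before the decision are 3 + 3·P(X ≥ 1) as written and 3 + 3·P(X = 1) with the restriction. This falls from 3.81 to 3.73 at 10%, from 4.46 to 4.15 at 20%, and from 5.63 to 4.13 at 50%.

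**Step 4: the other rules in the protocol.**

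- The 3+3 table in Section 3.1 adds three subjects at 1 of 3. It has no row for 2 or 3 of 3.
- Arm C at the RP2D: "Should a DLT be observed in the first three subjects at the RP2D of CyPep-1, an additional three subjects in this dose group" are included. Then: "In case that two or more subjects experience DLTs at RP2D of CyPep-1, a recommendation to dose de-escalate" comes from the DEC, with no denominator of six. DEC review after the first three is not conditional on there being no DLTs.
- Arm D: "In the occurrence of AEs fulfilling DLT criteria or other safety alters, the DEC will convene to review the safety data".

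The one arm that adds pembrolizumab therefore has a later written DEC trigger than Arm C at the RP2D or Arm D.

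**The case against.** The best defence is that sensible conduct would prevent this, and that the text can be read that way. The count out of six could be a running count, reached when the second TLT occurs. The review after the first three is described as covering TLTs, which would have little purpose if it took place only when there were none.

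There are also general safeguards. Section 3.1.1 lets the DEC de-escalate in Phase IIa on available safety data. All investigators or their designees sit on the DEC, so those who see the TLTs are members. Section 3.4 provides for an enrolment hold, and Section 7.1.7 has toxic deaths notified to the DEC immediately. SAP Section 7.3 places DEC analyses in a Cohort Management Plan that is not among the documents and might contain a 2-of-3 rule.

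These points lower the practical risk, but they do not repair the rule. None of the safeguards in the documents sets a TLT count that pauses dosing before subject 4. The running-count reading is possible, but it does not remove the instruction to add three subjects after any TLTs. The 24-hour stagger might continue for subjects 4 to 6, although Section 1.9.3 lists it only for the first three in this arm; in either case 24 hours is far short of the 6-week TLT window.

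Two further objections stand in part. Phase I monotherapy had no DLTs (Sections 1.6.1 and 5.3.4), so low rates may be more likely, though Phase I did not test the combination. Averaged over all outcomes, the extra TLTs are then few: 0.028 × 0.3 = 0.008 at 10% and 0.104 × 0.6 = 0.06 at 20%. And the Arm C comparison is not perfect, since a single DLT there can be read as at least one. The finding does not depend on that comparison.

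**Conclusion.** The concern holds. Followed as written, the rule exposes three more subjects to a dose at which 2 or 3 of 3 have had a TLT, before the stated trigger for the DEC and with no possibility of reversing the referral. That conclusion is logical and needs no assumed rate. Its size does: the frequencies assume independent subjects with a common TLT rate between 10% and 50%, every TLT counted, and a literal reading of the expansion step. At the low end the situation is uncommon. It should still be corrected, because the subjects affected are those at highest risk and the correction sacrifices nothing in the decision rule.

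**What to change.** In the Arm B text of the protocol synopsis, Protocol Section 3.1 and SAP Section 6.1:

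- Add three subjects only when exactly one of the first three has a TLT. This presumes that all three have completed the 6-week window.
- Require DEC review as soon as a second TLT occurs, whether among three or six subjects, and start no further subject until the DEC has made its recommendation. The DEC keeps its freedom to continue or de-escalate.
- Check that the Cohort Management Plan says the same.

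The cost is wording only. The sample size of 15 and the probability of clearing the RP2D do not change. The downside is a possible earlier DEC meeting and a pause in dosing. The documents do not say whether the Arm B run-in is finished. If it is, the clinical trial report should state how many TLTs occurred in the first three subjects and how the rule was applied.

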3.1.1 Dose Escalation Committee

The decisions on dose escalation and CyPep-1 MTD/RP2D will be taken by the Dose Escalation Committee (DEC) after reviewing safety data (including DLTs) from all subjects who have entered Phase I of the trial and have completed the DLT observation period.

The DEC will review all data after all subjects in the highest dose cohort completed DLT observation period and before enrolment of subjects in the expansion cohort at RP2D in monotherapy and combination with pembrolizumab cohort can be initiated.

For Phase IIa of the trial, the decision to de-escalate the dose of CyPep-1 based on observed the severity and relatedness of safety events (DLT/TLT criteria for CyPep-1) and to what dose (either dose level of the next lowest dose level from Phase I or 50-70% of current dose level), will also be made by the DEC after reviewing available safety data (including TLTs). Dose modifications for pembrolizumab in the combination arm will also be taken into consideration (refer to [Section 5.3.6](#)).

Based on the review of this data, recommendations will be made regarding the further conduct and the scientific and ethical integrity of the trial.

The DEC is comprised of all the investigators or designees, as well as the medical monitor and representatives of the sponsor. The DEC, chaired by the medical monitor, will strive for a consensus opinion regarding the data reviewed. If DEC consensus is not possible, the DEC chair will assemble and present majority and dissembling opinions for all recommendations considered. If any of the DEC members cannot be present during the meeting due to the short notice, the DEC will be held (not postponed) provided that a minimum of 2 members are present. The DEC members may be allowed to provide their recommendations electronically to the DEC chair, prior to the meeting.

At the end of the DEC teleconference, the DEC will provide one of the following recommendations to the sponsor:

1. The trial is proceeding in line with the trial protocol.
2. The trial is not proceeding in line with the trial protocol and/or there is a possible change in the benefit/risk ratio.

The sponsor will act upon these recommendations as appropriate, i.e., the final decision will rest with the sponsor. The sponsor designee will notify the trial team (i.e., the responsible project manager at [REDACTED]) of the final decision regarding the DEC recommendations, including any actions to be taken. The [REDACTED] project manager will communicate the DEC recommendations and/or final decision of the sponsor to all investigators, Independent Ethics Committees (IECs) and Competent Authorities (CAs), if applicable.

